2.3 Sample Size Determination and Power

The sample size of this study is estimated based on following assumptions according to global pivotal study DEBIO 8206-CPP-301 [Klein 2016].

- Expected outcome for the proportion of children with a suppressed LH response to the GnRH stimulation test (stimulated peak serum LH ≤ 5 IU/L) at Month 6 is 93%;
- Null proportion is 80%;
- An exact binomial test of a proportion with a one-sided nominal significance level of 0.025 and power =85%;
- Expected common dropout rate =5%.

Under these assumptions, approximately 66 participants (Power Analysis and Sample Size

(PASS) software)) are planned to be enrolled into the study to ensure there are 62 treated participants to confirm the efficacy of the triptorelin 6-month formulation by the proportion of children with a suppressed LH response to the GnRH stimulation test at Month 6.

2.4 Randomisation and Blinding (if applicable)

This is a non-randomised, open-label study. The study treatment assignment will be known to the participants, investigators, study centres, Sponsor, and any Service Provider (SP) affiliated with the study. Access to the data in the Electronic Data Capture (EDC) system is controlled and limited only to authorised personnel for specified data review.

2.5 Schedule of Assessments

Schedule of assessments is presented in Section 8 from the protocol.

2.6 Change from Statistical Section of the Protocol

There is no change in SAP from statistical section of the protocol.

3 PLANNED ANALYSES

3.1 Data Monitoring

No independent Data Monitoring Committee (DMC) will be used in this study.

3.2 Interim Analysis / Primary Analysis

No interim analysis will be performed. If an unplanned interim analysis is deemed necessary, the appropriate sponsor medical director, or designee, will be consulted to determine whether it is necessary to amend the protocol.

No primary analysis will be performed for the primary endpoint at month 6.

3.3 Final Analysis

Final analysis will be done when all participants complete study (Month 12) and after database lock.

4 ANALYSIS SETS

The following populations will be used during statistical analyses:

- **Screened** population: All participants screened (i.e. who signed the ICF).
- **Safety** population: All participants who receive at least one dose of study intervention and have at least one post-baseline safety assessment.
- **Intention-To-Treat** population (ITT): All participants who receive at least one dose of study intervention.
- **Modified Intention-To-Treat population (mITT)**: All treated participants having a Month 6 post-baseline assessment of the primary efficacy endpoint.
- **Per protocol** set (PPS): All participants in the mITT after exclusion of the participants who had major protocol deviations that could potentially affect the primary efficacy endpoint outcome for the participants.
- **PK** set (PKS): All participants who receive at least one dose of study intervention and have at least one valid triptorelin concentration.

5 STATISTICAL METHODS/ANALYSES

The statistical analyses will be performed in accordance with ICH E9 guideline and guidelines presented in Section 8.

TigerMed will perform the statistical analysis of this study under the supervision of the Biometry department of IPSEN.

5.1 General Considerations

The precision of the measurement for each continuous variable will be used to determine the number of decimal places to present in tables, figures, and derived listings. Unless otherwise specified, min and max values will be reported with the same decimal as the units of measure; the mean, median and standard deviation (SD), will be reported to 1 greater decimal place, all of them will not be greater than 4 decimal places. Any values that require transformation to standard units (metric or International System [SI]) will be converted with the appropriate corresponding precision.

Percentages of categorical variables will be presented to 1 decimal place unless otherwise specified.

For laboratory values data below the lower limit of quantification (LLOQ) like “<xxx” or “<=xxx”, or above the upper limit of quantification (ULOQ) like “>xxx” or “>=xxx”, LLOQ or ULOQ (xxx) will be used for calculation of descriptive statistics. The original laboratory values (“<xxx”, “<=xxx”, “>xxx” or “>=xxx”) are presented in the listings.

All statistical analyses will be performed using the SAS® software version 9.4 or above version.

5.1.1 Outputs Presentation

5.1.1.1 Tables Header

Since this is a single-arm study, all summary tables will be presented by Female, Male and Overall.

5.1.1.2 Presentation of Gender Group

Tables, Figures and Listings (TFLs) will be displayed using the following gender group labels, in the order presented: Female, Male, Overall.

5.1.1.3 Presentation of Visits / Timepoints

Summaries by visit will be presented using visit number as collected in the Electronic Case Report Form (eCRF).

Visits in the TFLs will be presented as follows and in the following order:

| Long Visit Name | Short Name |
|---------------------|------------|
| Screening (Visit 1) | Scr |
| Baseline | Bsl |
| Month 3 (Visit 3) | M3 |
| Month 6 (Visit 4) | M6 |
| Month 9 (Visit 5) | M9 |
| Month 12 (Visit 6) | M12 |

5.1.2 Descriptive Statistics

All raw and derived variables will be listed and described using summary statistics. For categorical variables, summary statistics will be displayed using descriptive statistics by frequency count and percentages by category. The missing category will be presented if there is at least one missing category for at least one gender group. Except otherwise specified, participants with missing data will be included in the calculation of percentages. For quantitative variables, summary statistics will be displayed using descriptive statistics by number of observations, mean, SD, median, minimum and maximum. Missing data will be displayed.

5.1.3 *Baseline Value*

Unless otherwise specified, baseline is defined as the last non-missing measurement taken prior to first IMP administration (including unscheduled assessments). If the assessment time and/or IMP administration time is not collected, the assessment performed on the same day as the first IMP administration will be considered as baseline.

5.1.4 *Reference Start Date and Study Day*

Reference start date is defined as the day of the first IMP administration.

The day of the first IMP administration will be Day 1. Study day will be calculated as:

- The difference between the event date and the reference date plus one day, if the event is on or after the reference date.
- The difference between the event date and the reference date, if the date of event is prior to the reference date.

Study day will appear in any listings where an assessment date or event date appears.

In case of partial or missing event date, study day will appear missing while any associated durations will be presented based on the imputations described in appendix A2.

5.2 Disposition and Analysis Sets

Following disposition summaries and listings will be provided:

- Summary table with the number and percentages of treated participants per gender and site on the ITT population,
- Summary table with the number and percentage of participants screened, screen failed, reason for screen failures, treated, completed, withdrawn and reason for withdrawal, on the screened population,
- Summary table on duration of participant participation in the study. The definition of the duration of participant participation is from date of consent to the last study visit on the ITT population,
- Listing of dates of visit including duration of participant participation for the treated participants on the ITT population,
- Listing of screen failure participants on the screened population,
- Listing of withdrawal participants on the ITT population.

Following population summaries and listings will be provided on the ITT population:

- Listing of participants violated inclusion criteria,
- Listing of participants fulfilled exclusion criteria,
- Summary of the number and percentage of participants in each analysis population by gender group, based on all treated participants with reasons for exclusion from each analysis population,
- Listing including flag for each analysis population and reason for exclusion from each population.

5.3 Protocol Deviations

An exhaustive list of major protocol deviations that may occur during the course of the study and any action to be taken regarding exclusion of participants from the PPS population is defined in Protocol Deviation Assessment Plan. Major protocol deviations will be determined before database lock of the study, finalised during the data review meeting and documented in a separate document.

Following protocol deviation summary and listing will be provided on the ITT population:

- Number and percentage of participants with major protocol deviations by deviation category (see DV section of Standard Study Data Tabulation Model (SDTM) user guide).
- Number and percentage of participants with major protocol deviations related to COVID-19 by deviation category.
- Listing of major protocol deviations.
- Listing of all protocol deviations by deviation class (e.g. minor/major).
- Listing of all COVID-19 pandemic related protocol deviations by deviation class (e.g. minor/major).

5.4 Demography and Other Baseline Characteristics

All demographic and baseline characteristics summaries and listings will be provided for the ITT, mITT, PPS and safety population. No statistical comparison between gender groups will be performed.

Following summaries will be provided on:

- Demographic variables (age, ethnicity, race),
- Other baseline characteristics (height, weight, BMI, pubertal stage, growth velocity, bone age, chronological age, the difference between bone age and chronological age, ratio of BA:CA),
- Disease characteristics (Age of diagnosis, Time from initial diagnosis of CPP, GnRH-stimulated LH peak, GnRH-stimulated FSH peak, Basal LH, Basal FSH, oestradiol levels and uterine length for girls, testosterone levels and testicular volume for boys).

Listings will also be provided for all the summaries listed above.

5.5 Medical History, Non-drug Therapies, Medications and Surgical Procedures

Medical and surgical history, non-drug therapies and surgical procedures will be coded using the latest version of Medical Dictionary for Regulatory Activities (MedDRA) in effect within IPSEN at the time of database lock. Medications will be coded using the latest version of World Health Organization-Drug dictionary in effect within IPSEN at the time of database lock.

Medication, non-drug therapies and surgical procedures start and stop dates will be compared to the date of the first IMP administration to allow classification as either Prior only, Prior and Concomitant, or Concomitant only:

| | |
|-----------------------------------|--|
| Prior (P) | Start and stop dates prior to the date of the first IMP administration. |
| Prior and Concomitant (PC) | Start date before the date of the first IMP administration and stop date on or after the date of the first IMP administration. |
| Concomitant (C) | Start date on or after the date of first IMP administration. |

Summary tables on prior medications/non-drug therapies/surgical procedures will include “P” only, summary tables on concomitant medications/non-drug therapies/surgical procedures will include “C” and “PC”.

See detailed rules in appendix A2 for classification of prior and concomitant medication/non-drug therapies, surgical procedures in case of partial/missing date.

The therapeutic class will correspond to the second level of Anatomical Therapeutic Chemical (ATC) code, that is, corresponding to the first 3 figures.

Following summaries, presenting count and percentages of participants will be provided on the ITT population :

- Medical and surgical history by primary system organ class (SOC) and preferred term (PT),
- Prior medications (P) for the study indication by ATC class (ATC level 2) and preferred term PT,
- Concomitant medications (PC, C) for the study indication by ATC class (ATC level 2) and preferred term PT,
- Prior non-drug therapies (P) by primary SOC and PT,
- Concomitant non-drug therapies (PC, C) by primary SOC and PT,
- Prior surgical procedures (P) by primary SOC and PT,
- Concomitant surgical procedures (PC, C) by primary SOC and PT,

Listings will be provided for all the summaries listed above. These listings should include a flag indicating the category (P, PC, C) as described in the table above.

A prohibited medication listing be provided including the following drug: Oestradiol, Testosterone, GnRH analogues (other than triptorelin 6-month formulation),

medroxyprogesterone acetate, growth hormone or Insulin-like Growth Factor 1 (IGF-1), systemic or inhaled steroids (mild topical steroids are permitted) or anticoagulants or drugs which raise prolactin levels.

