6.8 Concomitant Therapy

Any medication or vaccine (including over the counter or prescription medicines, recreational drugs, vitamins, and/or herbal supplements) that the participant receives within 2 months before triptorelin administration or during triptorelin administration must be recorded on the eCRF along with:

- Generic or trade name
- Reason for use
- Dates of administration including start and end dates
- Dosage information including dose and frequency

The medical monitor should be contacted if there are any questions regarding concomitant or prior therapy.

The following concomitant medications are not permitted during this study:

- Any treatment or procedure with an effect on the metabolism or secretion of gonadotropins (LH or FSH) or sex steroids (oestradiol and/or testosterone) will be considered as a protocol violation
- All drugs mentioned as prohibited in the non-inclusion criteria remain prohibited during the study period: GnRH analogues (other than triptorelin 6-month formulation), medroxyprogesterone acetate, growth hormone or IGF-1, systemic or inhaled steroids (mild topical steroids are permitted) or anticoagulants.

- Drugs which raise prolactin levels should not be prescribed concomitantly as they reduce the level of GnRH receptors in the pituitary. When triptorelin is co-administered with drugs affecting pituitary secretion of gonadotropins, caution should be taken, and it is recommended that the participant's hormonal status be supervised.

6.8.1 *Rescue Medicine*

Not applicable

Approved

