9.4.1.3 Statistical/Analytical Methods

Statistical analyses will be performed by an external Service Provider, managed by the Sponsor's Biometry department.

Demographic and Other Baseline Characteristics

Descriptive summary statistics (n, mean, SD, median, minimum, maximum) and frequency counts of demographic and baseline data (medical history, concomitant disease, predosing AEs and ongoing medical history, prior and concomitant medications and therapies) will be presented for the ITT, mITT and PP sets, as well as the Safety population.

Participant Disposition and Withdrawals

The numbers and percentages of participants screened and included in each of the analysis populations will be tabulated overall and by centre. The reasons for participant exclusions from each of the populations and primary reasons for study discontinuation will be tabulated.

Adjustment for Country/Centre Effect

Descriptive analysis will be carried out to evaluate any possible centre effect.

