Concomitant medication will be coded by using World Health Organization Drug Dictionary (WHO-DD) version (version in use before database lock) and will be summarised with the number and percentage of participants receiving concomitant medication by drug class and preferred drug name.

Haematological and biochemical toxicities will be recorded and graded according to the NCI-CTCAE criteria, where available. The NCI-CTCAE Grades 3 and 4 haematology and biochemistry variables will be listed by participant and by visit.

Actual values and changes from baseline in clinic 1 laboratory tests, physical examinations and vital signs will be summarised using descriptive statistics at each visit. For laboratory data, abnormal values will be flagged in the data listings and a list of clinically significant abnormal values will be presented. Shift tables using the worst on-treatment grade will be presented for the number and percentage of participants with NCI-CTCAE grades.

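### SAP 5.5 limits the medication tables to drugs taken for the study indication, on ITT only, although the protocol commits to summarising all prior and concomitant medication and SAP 2.6 declares no change

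*SAP*

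**What the plan says.** **SAP 5.5** (medical history, non-drug therapies, medications and surgical procedures) introduces a list of summaries on the ITT population. Two of them concern medications: "Prior medications (P) for the study indication by ATC class (ATC level 2) and preferred term PT" and "Concomitant medications (PC, C) for the study indication by ATC class (ATC level 2) and preferred term PT". The neighbouring lines have no such limit, for example "Concomitant non-drug therapies (PC, C) by primary SOC and PT". The section then adds: "Listings will be provided for all the summaries listed above". It ends with a separate listing of prohibited medications.

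**Protocol 9.4.4** (Safety Analyses) says that concomitant medication "will be summarised with the number and percentage of participants receiving concomitant medication by drug class and preferred drug name". It does not mention indication, and the same section bases its summary tables on the Safety population.

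**Protocol 9.4.1.3** (demographic and other baseline characteristics) says that baseline data, including "prior and concomitant medications and therapies) will be presented for the ITT, mITT and PP sets, as well as the Safety population".

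**Protocol 6.8** sets what is recorded: "Any medication or vaccine (including over the counter or prescription medicines, recreational drugs, vitamins, and/or herbal supplements"), taken within two months before or during triptorelin administration.

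**SAP 2.6** states: "There is no change in SAP from statistical section of the protocol".

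**The concern.** The protocol collects all medication and promises tables of it. The SAP narrows those tables to drugs given for CPP and does not declare the narrowing. A programmer who follows SAP 5.5 would apply an indication filter to medications and to nothing else in that list. Antibiotics, analgesics, vaccines and any drug given to treat an adverse event would then appear in neither table.

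This is a single-arm trial of about 66 children, so there is no control group against which to judge adverse events. A table of co-medication by class and preferred name is one of the few summaries that helps a reader see what else the children were taking. The protocol places that table among its safety analyses.

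**Working it through.** No arithmetic applies: the point depends on no rate, error level or sample size. The check is a comparison of texts.

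**1. Scope of the tables**

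| | Protocol | SAP 5.5 |
|---|---|---|
| Concomitant medication | All, by drug class and preferred name (9.4.4) | Only for the study indication, by ATC level 2 and preferred term |
| Prior medication | Presented without limit by indication (9.4.1.3) | Only for the study indication |
| Population | ITT, mITT, PP and Safety (9.4.1.3); Safety for the safety tables (9.4.4) | ITT |

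Both scope and population differ.

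**2. Is the missing table planned elsewhere in the SAP?** SAP 5.4 covers the four populations, but its items are demographic variables, other baseline characteristics and disease characteristics. Medications are not among them. SAP 5.8 (Safety) covers exposure, adverse events, local tolerability, laboratory data, vital signs, physical examination and pregnancy, and names no medication table. So no table named in the SAP gives the all-medication summary.

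**3. Do the listings fill the gap?** The listings named in SAP 5.5 are defined by reference to the summaries above them, so they carry the same limit. Three other texts bear on this:
- SAP 5.1.2 says in general terms that all raw and derived variables will be listed and summarised.
- SAP 5.8.1 says that all safety data will be in participant listings.
- The prohibited-medication listing at the end of SAP 5.5 applies whatever the indication. It covers oestradiol, testosterone, other GnRH analogues, medroxyprogesterone acetate, growth hormone, IGF-1, systemic or inhaled steroids, anticoagulants and prolactin-raising drugs.

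The first two may yield a full listing. None of the three specifies a table by class and preferred name.

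**4. What would the restricted tables contain?** Exclusion criterion 6 bars prior or current GnRH agonist, medroxyprogesterone acetate, growth hormone and IGF-1. Protocol 6.8 prohibits these on study and treats anything acting on gonadotropins or sex steroids as a protocol violation. Protocol 2.2 sees no effective alternative to prolonged-release GnRH treatment for CPP. Few permitted concomitant drugs could therefore be for CPP. For prior drugs the argument is weaker: criterion 6 names four drug groups, and Protocol 6.8 also records herbal, vitamin and over-the-counter products, some of which could have been taken for CPP before entry.

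**5. Is the difference declared?** SAP 2.6 declares no change, so it is not.

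**The case against.** The best defence is that this may be a drafting slip with little effect. The sentence in SAP 5.5 that assigns the prior and concomitant categories to tables has no indication limit. Coding and classification apply to all medications, and the adjacent lines are unrestricted. The table shells are a separate document, not available here, and may contain a full table. The tables are descriptive and touch no test.

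Much of this is fair, and it rules out several stronger conclusions that a reader might draw:

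- *That all other drugs go unreported.* The documents do not support this. SAP 5.1.2 and 5.8.1 can be read as requiring a full listing, and the listing sentence in SAP 5.5 does not exclude further listings.
- *That the restricted tables will be empty, or nearly so, for the 66 children.* No document gives a count. The expectation is an inference from the eligibility and prohibition rules, reasonable for concomitant drugs and less so for prior ones.
- *That hormone and growth results cannot be read against co-medication.* The prohibited-drug listing covers the hormone- and growth-active drugs that the protocol itself names, whatever they were given for.

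The defence does not remove the conflict. The sentence on categories says which records count as prior or concomitant. The two bullets name the actual tables, and both carry the limit. General sentences on listing and summary statistics do not define a table by class and preferred name. Shells should follow the SAP, and the SAP text does not plan this table. If the limit is a slip, the same correction is needed.

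**Conclusion.** The point holds as an undeclared conflict between the SAP and the protocol. As written, SAP 5.5 omits the all-medication count-and-percentage tables to which Protocol 9.4.4 and 9.4.1.3 commit, uses one population where 9.4.1.3 names four, and makes the statement in SAP 2.6 inaccurate.

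The size is minor. The loss falls mainly on reading adverse events against co-medication. The primary endpoint, its test and the error rate are untouched. The conclusion assumes that the programming follows the bullets in SAP 5.5 and that the unseen shells do not already restore the full tables. The conflict between the two texts stands however many children would appear in the restricted tables.

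**What to change.** In SAP 5.5, delete the limit to the study indication from both medication bullets, so that all prior and all concomitant medications are tabulated and, through the listing sentence, listed. Present these tables on the ITT, mITT, PP and Safety populations, as Protocol 9.4.1.3 says; this also gives the Safety-population table that 9.4.4 calls for. If the sponsor prefers fewer populations or a narrower scope, state the reduction and the reason in SAP 2.6. Check the shells against the revised text.

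No new data are needed, since Protocol 6.8 already has every medication recorded. The cost is longer descriptive tables and, if all four populations are kept, up to eight tables (2 × 4) in place of two.
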